Document Title: Study Protocol

Protocol Title: Menopausal Sleep Fragmentation: Impact on Body Fat Gain Biomarkers in Women

Protocol #: MGB Human Research Committee #2016P002821

NCT: 03047330

Document date: January 3, 2024

**PARTNERS HUMAN RESEARCH COMMITTEE
PROTOCOL SUMMARY**

Answer all questions accurately and completely in order to provide the PHRC with the relevant information to assess the risk-benefit ratio for the study. Do not leave sections blank.

PRINCIPAL/OVERALL INVESTIGATOR

[name], MSc

PROTOCOL TITLE

Menopausal Sleep Fragmentation: Impact on Body Fat Gain Biomarkers in Women

FUNDING

National Institute of Health – National Institute on Aging

VERSION DATE

1/3/2024

SPECIFIC AIMS

Concisely state the objectives of the study and the hypothesis being tested.

Aim #1: To determine the impact of menopause-related sleep fragmentation on metabolic and behavioral biomarkers of body fat gain using an experimental sleep disruption paradigm to fragment sleep in healthy female volunteers

Hypothesis 1a: Experimental sleep fragmentation will result in an adverse adipokine profile as a metabolic biomarker for body fat gain

Hypothesis 1b: Experimental sleep fragmentation will result in increased hunger and caloric intake

Hypothesis 1c: Sleep disruption due to hot flashes will result in an adverse adipokine profile and increased hunger and caloric intake

Aim #2: To examine if hot flashes are associated with metabolic and behavioral biomarkers of body fat gain using an experimental hormone suppression paradigm in healthy women

Hypothesis 2: Hot flash frequency will correlate with a worse adipokine profile and increased hunger and caloric intake

Aim #3: To determine if estradiol withdrawal adversely affects metabolic and behavioral biomarkers of body fat gain using an experimental hormone suppression paradigm in healthy women

Hypothesis 3: Experimental withdrawal of estradiol will correlate with a worse adipokine profile and increased hunger and caloric intake

Aims 1–3 Exploratory Hypotheses:

1) Experimental sleep fragmentation mimicking menopause-related sleep disruption will reduce resting energy expenditure. 2) Baseline levels of total body fat and visceral adiposity will influence

the metabolic and behavioral response to sleep fragmentation, hot flashes, and estradiol withdrawal. 3) Negative mood state will correlate independently with an adverse adipokine profile and increased hunger and caloric intake.

BACKGROUND AND SIGNIFICANCE

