Provide a brief paragraph summarizing prior experience important for understanding the proposed study and procedures.

Obesity is highly prevalent in midlife and older women. Over 50% of women gain body fat during the menopause transition, unrelated to chronological aging, increasing the likelihood of cardio-metabolic diseases after menopause. While these body composition changes are attributed to E2 withdrawal, other menopause-related factors likely contribute to adiposity because: 1) body fat gains are not uniform despite universal progression to hypo-estrogenism, and 2) body fat accrues during the MT, when E2 continues to be produced intermittently. Sleep fragmentation related to HF occurs in almost half of midlife women and may be an important factor driving risk for body fat gain, but its impact on metabolic and behavioral biomarkers of body fat gain has not been investigated. This sleep fragmentation results commonly from HF, which occur in 2/3 of midlife women. In other populations, individuals who sleep less are heavier and have adverse adipokine profiles. Experimental studies restricting TST show that sleep reduction lowers leptin, and increases ghrelin, appetitive drive, and caloric intake, key biomarkers of adiposity, with some sex differences in effects. However, TST is not reduced in HF-related sleep fragmentation, and metabolic effects of sleep fragmentation have received limited investigation in humans, although animal studies show that sleep fragmentation adversely effects adipokines and eating behaviors. The goal of the current proposal is to determine the impact of HF-related sleep fragmentation, as well as that of HF and E2 withdrawal, on body fat gain in women. *Given the prevalence of HF and associated sleep disruption, identifying the impact of these core menopause symptoms on body fat gain will inform health promotion strategies to prevent gains in body fat in midlife women, thereby reducing cardio-metabolic diseases in aging women.*

RESEARCH DESIGN AND METHODS

Briefly describe study design and anticipated enrollment, i.e., number of subjects to be enrolled by researchers study-wide and by Partners researchers. Provide a brief summary of the eligibility criteria (for example, age range, gender, medical condition). Include any local site restrictions, for example, “Enrollment at Partners will be limited to adults although the sponsor’s protocol is open to both children and adults.”

[figure not shown]
Overview

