Obesity is highly prevalent in midlife and older women, with rates increasing markedly after age 40 and abdominal adiposity increasing in half of women during and after the menopause transition independent of age, but the factors that cause these changes are not well understood. Reduced total sleep time has been shown to adversely impact biomarkers of obesity, but the effect of menopause-related sleep fragmentation, which occurs in >40% of midlife women and is characterized by sleep interruption secondary to hot flashes, on metabolism and eating behaviors is not known. The broad goal of this proposal is to isolate the impact of menopause-related sleep disruption, as well as menopause-related hot flashes and estrogen withdrawal, on behavioral and metabolic biomarkers of body fat gain, results of which will inform strategies to prevent gains in body fat, thereby improving cardiovascular and metabolic health outcomes in women.

EQUITABLE SELECTION OF SUBJECTS

The risks and benefits of the research must be fairly distributed among the populations that stand to benefit from it. No group of persons, for example, men, women, pregnant women, children, and minorities, should be categorically excluded from the research without a good scientific or ethical reason to do so. Please provide the basis for concluding that the study population is representative of the population that stands to potentially benefit from this research.

The study population is restricted to non-pregnant premenopausal women, the population for whom

the information obtained in this study is relevant. Pregnant women are excluded because of risks with study medication to the unborn fetus. Children under 18 are excluded because the study is not relevant to pre-pubertal children and the hypothalamic-pituitary-ovarian axis is in flux in many post-pubertal teenage girls, as reflected by frequent menstrual-cycle abnormalities in this population. The age requirements are that women must be within 18-45 years of age in order to study experimentally induced hot flashes in women who are close to natural menopause. Men are excluded because the hormonal changes (e.g., estrogen) that occur with GnRH agonists differ between women and men and these outcomes are important components of this study. Minority populations are included.

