To address **Aim 1** (*impact of menopause-related sleep fragmentation on metabolic and behavioral biomarkers of body fat gain*), the mean levels in each endpoint in response to experimentally fragmented sleep (**Hypothesis 1a & 1b**) will be examined using repeated-measures generalized linear mixed-model regression. Models will incorporate the 2 SB contrasts addressing **Hypothesis 1a and 1b** to simultaneously compare the impact of sleep fragmentation in the HF-free, estrogenized environment (**SB_{SF1} vs. SB_{UD1}**), and hypo-E2 environment with stable HF levels (**SB_{SF2} vs. SB_{UD2}**); exploratory analyses will adjust for HF, either categorized (e.g., any versus none) or number of HF. If there is an omnibus effect of experimental sleep fragmentation, we will conduct post-hoc analyses on each SB contrast to explore whether the impact of experimental sleep fragmentation is consistent across hormonal and HF contexts. To address **Hypothesis 1c**, mean levels in outcomes will be contrasted **SP_{UD3} vs. SP_{UD1}** to assess the impact of sleep disruption related to HF in the environment without experimental sleep fragmentation, comparing those developing HF (expected N=26) with those who do not develop HF; analyses will adjust for initial E2 level.

Aim 2 (*impact of HF on metabolic and behavioral biomarkers of body fat gain*) will be examined using a repeated-measures generalized linear mixed-model regression analysis to determine the effect of HF on mean levels of in metabolic and behavioral biomarkers. The regression will include SB contrasts that assess the impact of HF in the presence (**SB_{SF2} vs. SB_{SF1}**) and absence (**SB_{UD2} vs. SB_{UD1}**) of experimental sleep fragmentation. If an omnibus effect of HF is observed, post-hoc analyses will be conducted on each SB contrast to explore whether the impact of HF is consistent across sleep fragmentation contexts. Additional analyses will substitute objectively measured HF or night-time only HF.

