Sample size: Forty subjects will complete all study procedures. Sample size calculations are based on pilot data correlations between the change in the number of EEG arousals and change in leptin levels from before to after receiving GnRHa. The observed Pearson and Spearman correlations are $r=-0.44$ and $r_s=-0.36$. The detectable correlation is $r=-0.43$ for a sample size of 40 and $r=-0.52$ for the subgroup analysis ($n=26$) in **Hypothesis 1c** ($\alpha=0.05$, 80% power). Because it takes 3 months (screening/menstrual tracking plus 2 months of active procedures) for each subject to complete the study and data analysis time is required after all procedures are completed, accrual is expected to be achieved in the first 39–42 months of the Award. The expected accrual rate of 1.1 subjects per month is therefore similar to that which [REDACTED] achieved in prior healthy volunteer studies with a similar number of in-lab nights. This rate is lower than the 1.7/month that [name] achieved with healthy volunteers to leuprolide studies but with less intensive procedures. To ensure that accrual proceeds as planned, we will advertise widely using postcards we have used to enroll 2.4 women/month to menopause studies and which colleagues used to enroll 2.2 healthy volunteers/month to a study with fewer nights in the sleep lab.¹⁴² Based on previous experience, we expect to consent up to 130 subjects in order to have 40 study completers, given that up to 10 women may not be eligible after completing screening procedures and an additional 8 women may decline to receive leuprolide after completing SB#1, and because some women will participate in pilot procedures only.

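### Hypothesis 1c is about sleep disruption due to hot flashes, but its written test contains no sleep measure, and the power stated for it describes a different analysis

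*SAP*

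**What the plan says.** The Protocol (Specific Aims) words Hypothesis 1c as "Sleep disruption due to hot flashes will result in an adverse adipokine profile and increased hunger and caloric intake". The exposure is disturbed sleep, with HF as its cause.

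The SAP (Aim 1) assesses 1c by contrasting mean outcomes between a pre- and a post-leuprolide undisturbed period, "comparing those developing HF (expected N=26) with those who do not develop HF", with adjustment for initial E2. It says the purpose is to assess HF-related sleep disruption. No arousal count, number of awakenings or wake time after sleep onset enters the model.

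The SAP (Sample size) says: "Sample size calculations are based on pilot data correlations between the change in the number of EEG arousals and change in leptin levels". It reports pilot correlations of -0.44 (Pearson) and -0.36 (Spearman). The detectable correlation is given as -0.43 for 40 women and -0.52 "for the subgroup analysis" of 26 women under 1c, at alpha 0.05 and 80% power.

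The only other planned use of HF-related sleep disruption is an exploratory adjustment under Aim 3, which names no measure.

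**The concern.** Developing HF is a proxy for HF-disturbed sleep, and the Protocol's own figures show that the two are not the same. Background and Significance says of HF-related fragmentation: "This sleep fragmentation results commonly from HF, which occur in 2/3 of midlife women". The same section puts the fragmentation itself lower: "Sleep fragmentation related to HF occurs in almost half of midlife women". A later section (Importance of the knowledge to be gained) refers to "menopause-related sleep fragmentation, which occurs in >40% of midlife women".

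The Protocol's stated goal is to isolate sleep disruption from HF and from estrogen withdrawal. If women with HF differ from women without, the written 1c test cannot say whether disturbed sleep or HF themselves are responsible. If they do not differ, one possible reason is that some women with HF slept well. The quoted power does not help in judging either result, because it belongs to a correlation and the written test is a difference between two groups.

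**Working it through.** **Inputs.** From the SAP: 40 completers, 26 expected with HF, alpha 0.05, 80% power, pilot r = -0.44. By subtraction: 40 - 26 = 14 women without HF. Two-sided testing is inferred, because the one-sided values (0.387 and 0.477) do not match the stated ones.

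**1. The plan's own figures.** For a correlation with k covariates, Fisher's z gives detectable |r| = tanh[(1.960 + 0.842) / sqrt(n - 3 - k)].
- n=40, k=0: tanh(2.802 / sqrt 37) = 0.431. Stated: 0.43.
- n=26, k=0: tanh(2.802 / sqrt 23) = 0.526; the bias-corrected version gives 0.519. Stated: 0.52.

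Both figures reproduce. The arithmetic is correct for a correlation.

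**2. The comparison as written.** For a difference in change scores, 26 vs 14, unadjusted:
- Normal approximation: d = 2.802 x sqrt(1/26 + 1/14) = 2.802 x 0.3315 = 0.93 SD.
- Noncentral t on 38 degrees of freedom: d = 0.95 SD.
- Power is about 31% at 0.5 SD and 65% at 0.8 SD.

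The unit is the between-woman SD of the change score. The documents give no value for it, so the result stays in SD units.

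**3. Power of an arousal analysis at the pilot correlation.** Power = Phi[atanh(0.44) x sqrt(n - 3 - k) - 1.960], with atanh(0.44) = 0.472. The value 0.44 is treated as the adjusted correlation when k > 0.

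| Covariates | n=26 | n=40 |
|---|---|---|
| none | 62% | 82% |
| initial E2 | 60% | 81% |
| initial E2 and HF frequency | 58% | 80% |

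The documents do not say that the pilot correlation came from women with HF only. If arousal change varies less among them, r falls. With u the ratio of its SD to that in the full group, r' = 0.44u / sqrt(1 - 0.44² + 0.44²u²). Assuming u = 0.8 gives r' = 0.36 and 45% power at n=26 without covariates (42% with two). Assuming u = 0.7 gives r' = 0.32 and 37% (34% with two).

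**4. Why HF frequency belongs in that model.** I simulated n=26 with no sleep effect at all, HF frequency correlating 0.52 with the outcome, and a correlation between arousals and HF frequency of 0.3, 0.5 or 0.7 (an assumed range). A model with arousals but not HF frequency declares an arousal effect in about 12%, 25% and 46% of runs. With HF frequency included, the rate is about 5% throughout.

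**The case against.** The strongest reply is that 1c should not be read alone. Hypotheses 1a and 1b test fragmentation before leuprolide, when women are free of HF. On fragmented nights sleep is interrupted to one target level in every woman, so Aim 2's contrast of fragmented nights before and after leuprolide looks at HF with sleep disruption held roughly constant. A direct HF effect should appear on fragmented and undisturbed nights alike, and an effect through sleep mainly on undisturbed nights. Aim 2 also substitutes night-time HF, and the SAP commits to reading consistency across contexts. This stands in part: a reader might infer that the trial has no means of separating the two routes, and that goes too far. But the help is indirect, the context-by-context step is post hoc and depends on an omnibus effect, and none of it puts a sleep measure into 1c.

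A second reply is that the correlation may be a study-wide planning device, since the n=40 figure also sits beside mean contrasts. That is fair. A reader might infer from n=26 that an arousal analysis within the HF group was intended and left out; this is only one reading. On either reading, the figure attached by name to 1c does not describe the written test.

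A third reply concerns the prevalence figures. A reader might turn them into a share of women with HF whose sleep is disturbed (0.40/0.667 = 60% to 0.50/0.667 = 75%) and derive a power loss. They describe natural midlife, one is open-ended, and the trial enrolls leuprolide-treated women aged 18 to 45. They show that the two states differ; they do not size the loss here.

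**Conclusion.** The point holds on two counts. The written 1c test has no sleep measure and, by itself, cannot attribute a difference to disturbed sleep. The power stated for 1c (r = -0.52, n=26) belongs to an analysis that the SAP does not specify; the written 26 vs 14 comparison detects about 0.95 SD, assuming two-sided 0.05, 80% power, 14 women without HF and no covariate adjustment.

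Two further inferences are not supported. The sample-size arithmetic is not wrong: it reproduces. The SP_UD3 label in the 1c contrast does not show an error either. It is undefined in the readable text, but the schema is not shown and may define it. It should be checked, and nothing here rests on it.

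This should be fixed before analysis. I am sure of the mismatch and less sure of the power of the remedy, which depends on the pilot correlation carrying over as an adjusted correlation.

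**What to change.** 1. Keep the HF yes/no comparison, and describe it as the total effect of developing HF.
2. Add to 1c a regression of the change in each endpoint (post- minus pre-leuprolide undisturbed nights) on the change in polysomnographic EEG arousals, adjusted for initial E2 and HF frequency together. Report the model without HF frequency only as secondary, because it mixes sleep disruption with direct HF effects. Report the regression in the women with HF (n=26) and in all 40, and give the power of each at r = -0.44: about 58% and 80%, lower at n=26 if arousal change varies less among women with HF.
3. In the sample size paragraph, say which analysis r = -0.52 belongs to, and add the 0.95 SD detectable difference for 26 vs 14.

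The cost is SAP wording and one added analysis. Polysomnography is already planned for every inpatient night, so no new data are needed. The limits should be stated: the arousal analysis is observational, has modest power at n=26, and loses precision to the extent that HF frequency and arousals are correlated.

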Forty women ages 18–45 years will complete a protocol involving open-label treatment with standard-dose depot leuprolide to induce hypo-E2 in all women and generate HF in approximately 2/3, thereby mimicking menopause (see **Schema**). As part of the protocol, subjects will be admitted to the BWH Clinical And Translational Science Center/Center for Clinical Investigation (CCI) inpatient unit for a total of 10 nights over a 2-month period (see **Schema**). Assessments will be divided into 2 sleep blocks. Each SB includes 2 nights during which sleep is undisturbed and 3 nights during which sleep is experimentally fragmented. Using PSG, sleep patterns will be experimentally interrupted to the same target level for all subjects during all fragmented nights using auditory procedures to mimic the menopausal hot flash-associated sleep maintenance problem. The in-lab sleep blocks will be conducted: 1) during the mid-to- late follicular phase of the menstrual

cycle when E2 is high; and 2) after at least 4 weeks on leuprolide when HF are prominent in a subset of subjects.

Participants will be given a standardized eucaloric diet for several days preceding the inpatient admission, as well as for the first four days of the inpatient visit. On one day before admission, and on the final day of inpatient admissions, subjects will have an ad lib diet. Fasting adipokine levels will be measured and leptin levels will be obtained to determine the 24-hour leptin profile under standardized eucaloric diet conditions. Food intake and macronutrient composition will be assessed as key behavioral biomarkers for body fat gain when the diet is ad lib. Hunger will be measured under both eucaloric and ad lib dietary conditions. Secondary and exploratory measures of objective HF using skin conductance monitors, negative mood/affect, reward seeking behaviors, and appetite/food preference will also be obtained. Behavioral measures will continue to be assessed at home after the 2nd SB is complete.

Protocol Schema

Study Sample and Criteria

Informed consent will be obtained from up to 130 healthy non-pregnant premenopausal women 18-45 years who do not have hot flashes in order to have 40 women complete study procedures.

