metabolic and stress markers will be collected during each visit. Blood samples will be collected repeatedly up to every 30 minutes during each visit. Blood will be drawn without interrupting sleep using an approximately 72" long IV line from outside the room and a blood-sparing technique to minimize blood loss. If issues with the IV occur, then select samples, up to 2 per wake episode may be drawn via venipuncture. Core Body Temperature will be measured with an oral thermometer. Hunger will be measured under both eucaloric and ad lib dietary conditions by administering Hunger Visual Analog Scales. On the day of admission, reproductive hormone levels will be tested, a urine pregnancy test will be performed, and morphometric measures will be gathered. During the inpatient stay, subjects will complete various questionnaires and tasks (e.g. Food Preference Questions, the Dutch Eating Behavior Scale, the Positive and Negative Affect Scale, hot flash diaries, reward seeking behavior, PSQI, ISI, PHQ-8). After waking, subjects may complete the post-sleep questionnaire and the CCI IPM Exit Questionnaire, which are regularly administered by CCI inpatient unit staff. Subjects may also complete neurobehavioral testing administered automatically by the computers on the CCI inpatient unit. Throughout the inpatient portions of the study urine voids may be scheduled to be collected approximately every 3 hours when the subject is awake. Unscheduled urine voids during the day or overnight may also be collected. For each void, the urine volume will be measured, and aliquots may be saved for later hormonal, metabolite, or electrolyte analysis of analytes that may be affected by sleep fragmentation and/or changes in hormonal status. Urine samples will be collected and stored per standard techniques. Skin conductance may be measured using the Biolog skin conductance monitor. During the 4 days prior to admission, subjects will receive several days of eucaloric meals from the CCI Nutrition Service, and ad lib breakfast will take place at BWH in order to measure food intake. Subjects will be instructed to standardize their sleep patterns during the 4 days at home, and up to a week beforehand, to extend the standardized routine.

- **Undisturbed procedures only:** Bedtime and wake-up time will be fixed to an 8-hour standardized TST.

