Document Title: Statistical Analysis Plan

Protocol Title: Menopausal Sleep Fragmentation: Impact on Body Fat Gain Biomarkers in Women

Protocol #: MGB Human Research Committee #2016P002821

NCT: 03047330

Document date: January 3, 2024

Biostatistical Analysis

Analysis approach: Metabolic endpoints are: 1) fasting morning levels of leptin (primary), adipokines, ghrelin (secondary), and 2) the circadian leptin profile (exploratory), calculated as area under curve (AUC) to detect whether the overall profile is lower, as seen in sleep restriction studies,⁵³ and morning fasting AD levels. Behavioral endpoints are: 1) satiety (primary) and hunger (secondary) on a VAS scale, and 2) daily caloric intake during ad lib meals (exploratory). Analyses of each endpoint will be conducted in parallel as we seek to detect coherence among endpoints and focus on consistency across different outcomes in each hormonal and HF context.

Our experimental design, methodology, and analytic approach are robust and unbiased. While only women will be enrolled, analyses and interpretation of results will take into consideration age and other relevant biological variables. Key covariates will be measured and included as potential predictors in multivariate analyses, including specific *a priori* examination for age, race, BMI, SES, and stressful events to reduce unexplained variability in the outcomes.¹⁴¹ Importantly, within-subject analyses using each woman as her own control and expected low attrition based on our prior experience with similar protocols will minimize potential bias.

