To address **Aim 3** (*impact of estradiol withdrawal on metabolic and behavioral biomarkers of body fat gain*), the mean levels in each endpoint in response to estradiol withdrawal (**Hypothesis 3**) will be examined using repeated-measures generalized linear mixed-model regression. Models will incorporate the 2 estrogenized and hypo-E2 contrasts addressing simultaneously the impact of estradiol withdrawal in the unfragmented and fragmented sleep states. If there is an omnibus effect of estradiol withdrawal, we will conduct post-hoc analyses on each sleep state contrast to explore whether the impact of estradiol withdrawal is consistent across both sleep states. Exploratory analysis will include adjusting for HF – either categorical (yes/no or

none/infrequent/frequent) or continuous – and sleep HF-related disruption in the hypo-E2 state (second SB).

Exploratory Hypothesis #1 analyses will involve a repeated-measures generalized linear mixed-model regression similar to those proposed for the **Hypothesis 1a** analysis using the RQ as an indirect measure of resting EE as the dependent measure, and the same post-hoc paired contrasts and interaction terms for randomization order. **Exploratory Hypothesis #2** analyses will involve addition of interaction terms (between total body fat or visceral adiposity with sleep fragmentation, HF, or E2 withdrawal) to models described for **Aims 1–3**, to test for effect modification on each metabolic or behavioral endpoint. These analyses are by necessity exploratory in nature given the sample size of this complex experimental study. **Exploratory Hypothesis #3** will involve an omnibus repeated-measures regression model encompassing all 6 contrasts described in **Aims 1–3** with the PANAS Negative Affect scale score as the primary predictor and adjustment for fragmented versus undisturbed sleep given an expected association between sleep fragmentation and affect. Post-hoc analyses using paired t-tests on each SB contrast will be conducted to explore the potential variability of the impact of negative affect on each metabolic and behavioral biomarker across the sleep fragmentation, HF, and hormonal contexts. Psychological and cognitive factors driving eating behaviors on the DEBQ will also be explored.

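### Hypothesis 1c and Aim 2 do not separate hot flashes from estradiol withdrawal: 1c's only estradiol term is the initial level, and Aim 2 reuses Aim 3's before/after-leuprolide contrasts

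*SAP*

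**What the plan says.** The protocol's Overview describes leuprolide as given "to induce hypo-E2 in all women and generate HF in approximately 2/3" of them. With 40 completers (SAP, Sample size) and 26 expected to develop HF, about 14 stay HF-free.

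- **Hypothesis 1c (SAP, Aim 1)** looks at the change in undisturbed sleep from before to after leuprolide, "comparing those developing HF (expected N=26) with those who do not develop HF; analyses will adjust for initial E2 level". The block labels printed there do not match the two-block design. I read them as UD2 versus UD1.
- **Aim 2 (SAP)** fits a repeated-measures mixed model "to determine the effect of HF on mean levels of in metabolic and behavioral biomarkers". It continues: "The regression will include SB contrasts that assess the impact of HF in the presence" of experimental fragmentation (SF2 vs SF1) and in its absence (UD2 vs UD1). No E2 covariate is named.
- **Aim 3 (SAP)** states: "Models will incorporate the 2 estrogenized and hypo-E2 contrasts addressing simultaneously the impact of estradiol withdrawal", in both sleep states. It adds: "Exploratory analysis will include adjusting for HF". The reverse, an HF effect adjusted for the E2 level reached, is not planned.
- **Covariates (SAP, Analysis approach)** are named as "examination for age, race, BMI, SES, and stressful events to reduce unexplained variability in the outcomes". E2 is not among them.
- **Measurement (Protocol, Detailed Description of Sleep Blocks):** "On the day of admission, reproductive hormone levels will be tested". This applies to each admission, so a Sleep Block 2 value should exist.

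**The concern.** HF status is not randomised. Comparing changes between women with and without HF is a between-women comparison, so using each woman as her own control does not protect it.

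The documents supply both links of a confounding path. The protocol's risk section counts hot flashes among the consequences of ovarian suppression, so a less suppressed woman is more likely to be HF-free. Hypothesis 3 expects E2 withdrawal to worsen the same biomarkers. Sleep Block 2 E2 may therefore influence both HF status and outcome. Hypotheses 2 and 3 point the same way, so the bias would favour the HF hypothesis.

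Initial E2 measures the size of the withdrawal only if all women end at a similar low level. The plan expects this, but one reason it gives for the BMI limit is concern that leuprolide exposure could be too low. The visible text sets no laboratory criterion for suppression and does not say how unsuppressed women enter the analysis.

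In Aim 2 the same pairs of blocks carry two labels, HF and E2 withdrawal. Unless the model holds one constant, it cannot say which of them produced a change.

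**Working it through.** **The plan's own figures.** The SAP gives detectable correlations of −0.43 (n = 40) and −0.52 (n = 26) at α = 0.05 and 80% power. Two-sided Fisher z gives |r| = tanh[(1.960 + 0.842)/√(n − 3)], which is 0.431 and 0.526. With a t-based critical value and bias term it is 0.427 and 0.519. The figures reproduce and are not in dispute. They do not bear on which covariates are used.

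**Hypothesis 1c: size of the bias.** From the documents: 26 women with HF and 40 − 26 = 14 without. Assumed: the true HF effect is zero; m of the 14 are unsuppressed at Sleep Block 2 and have no withdrawal effect; all 26 HF women are suppressed; the E2-withdrawal effect is D, in SD of the change score.

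- Mean change with HF: D
- Mean change without HF: D × (14 − m)/14
- Apparent HF effect: D × m/14

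For m = 1, 2, 3 and 4 this is 7.1%, 14.3%, 21.4% and 28.6% of D. Simulated analyses of covariance (4000 runs per cell, initial E2 unrelated to later suppression) agree:

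| D | m | spurious HF effect, initial E2 only | false-positive rate |
|---|---|---|---|
| any of 0.5, 1.0, 1.5 | 0 | about 0 | about 5% |
| 0.5 | 2 | 0.07 SD | 6% |
| 0.5 | 4 | 0.13 SD | 7% |
| 1.0 | 2 | 0.15 SD | 6% |
| 1.0 | 4 | 0.29 SD | 12% |
| 1.5 | 4 | 0.43 SD | 19% |

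Adjusting for initial E2 hardly helps. At D = 1 and m = 4 the bias is 0.29 SD with or without it, and 0.27 SD if under-suppressed women start 0.5 SD higher. Adding error-free suppression status at Sleep Block 2 brings the bias to about 0 and rejection to about 5%. With a noisy log E2 value instead, at D = 1, the bias falls from 0.15 to about 0.08 SD (m = 2) and from 0.29 to about 0.11 SD (m = 4).

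**Aim 2: what identifies the HF effect.** Take D = 1 and a true HF effect of zero. In a within-woman regression with HF but no block or E2 term, HF-free women have no variation in HF and contribute nothing to its coefficient. The HF women contribute their whole before/after change, which is D. Results:

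| Model | m = 0 | m = 4 |
|---|---|---|
| HF, no block or E2 term | 1.0 | 1.0 |
| HF plus block term | 0 | 0.29 |
| HF plus error-free E2 status at each block | 0 | 0 |

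A random-intercept model also uses between-woman information and would return somewhat less than 1.0 in the first row. The confounding remains.

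**Form of the E2 term in Aim 2.** Sleep Block 2 E2 is one value per woman. As a main effect in a repeated-measures model it shifts her average level, not her change. A simulation assumed D = 1, m = 4, within-woman correlation 0.8, a block term, and E2 of about 10 if suppressed and 60 if not, entered as a log. Bias was 0.29 with initial E2 only, 0.27 with block 2 log E2 added as a main effect, 0.15 with time-varying log E2, and 0.08 with a block interaction.

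**Cost in precision.** The detectable HF difference, 26 versus 14, is 2.802 × √(1/26 + 1/14) = 0.93 SD. The squared correlation between HF and suppression status is 26m/[14(40 − m)]: 52/532 = 0.098 for m = 2 and 104/504 = 0.206 for m = 4. Dividing 0.93 by √(1 − 0.098) and √(1 − 0.206) gives 0.98 and 1.04 SD.

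**The case against.** The strongest reply is that the premise is assumed. The protocol expects every woman to become hypo-estrogenic and HF to vary all the same. It limits BMI and places Sleep Block 2 at least 4 weeks after the injection. If suppression is uniform, initial E2 does capture the size of the withdrawal and 1c is sound. This stands as far as it goes. A reader might infer that under-suppressed women will be present and will create a false HF effect. The documents report no such women and give no rate, so they support only that this can happen.

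The size can also be small. The m/14 figure puts every unsuppressed woman in the HF-free group with no withdrawal effect at all. Partial suppression, or such a woman having HF, reduces it. At D = 0.5 the bias is 0.07 to 0.13 SD for m = 2 to 4, against a detectable difference of 0.93 SD. This stands too.

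Third, the named covariates are introduced as examples, and the SAP promises in general terms to consider further biological factors. So it would be wrong to say that the plan adjusts for nothing but initial E2. But a general promise does not pre-specify an E2 term, and where the SAP does choose one it chooses the pre-treatment value.

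Finally, the block contrasts in Aim 2 may be meant to act as block terms. If so, Aim 2 is exposed only to the same conditional bias as 1c. The SAP does not say so. It presents those contrasts as measuring HF.

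**Conclusion.** The point holds as a gap in pre-specification.

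For 1c the bias is conditional. It is at most m/14 of the E2-withdrawal effect, 7% to 29% for m = 1 to 4, if the unsuppressed women are all HF-free. It is nil if suppression is equal. Both m and D are assumptions, since the documents give neither.

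For Aim 2 a reader might carry over the reassurance that full suppression removes the problem. It does not. Without a block or E2 term the HF coefficient absorbs essentially the E2 effect even when every woman is suppressed. With a block term Aim 2 falls back to the conditional bias of 1c.

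The planned Aim 3 adjustment for HF does not answer this, because it does not adjust the HF effect for the E2 level reached. The power figures are unaffected.

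**What to change.** Amend the SAP before the analysis:

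1. **Hypothesis 1c:** model the change score with Sleep Block 2 log E2 (or the log change in E2) alongside initial E2. Correct the block labels.
2. **Aim 2:** state that the model keeps a block (pre/post-leuprolide) term, so that differences between women in HF identify the HF effect. Add E2 as a time-varying covariate, using the value at each block, or as a block-by-E2 interaction, and choose between them in advance. One E2 value per woman as a main effect is not enough.
3. **Sensitivity analysis:** repeat both analyses in women who meet a laboratory definition of suppression fixed beforehand.
4. **Data:** confirm that the reproductive hormones tested on admission include E2, since the procedures text does not name it.

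If E2 is in that panel, no new data are needed. The price is some precision, with the detectable HF difference rising from about 0.93 SD to 0.98 SD (m = 2) or 1.04 SD (m = 4). That loss reflects real overlap between HF and E2. A single admission value is noisy, so the adjustment reduces the bias without fully removing it, and the report should say so.
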